Screening (Visit 1, duration: One hour): This visit will occur the same day as intervention visit. After subject arrives at TIRR a research personnel will meet him/her at the Motor Recovery Laboratory. The details of the study- specific procedures will be reviewed with the subject together. Subject will be screened for inclusion and exclusion criteria. Signed and dated informed consent will be obtained. Demographics, medical history, list of medications and modified ashworth scale score will be recorded. If the subject is female in child bearing ages, a urine pregnancy test results from primary care physician will be requested. A medication diary will be given to the subject and asked to document all changes in type and dosage of the medication he/she has been using throughout the study. This will allow us to differentiate a potential effect of a change in dosage or type of medication on movement recovery. After subject meets all Inclusion and Exclusion Criteria the randomization will be done by means of sealed, opaque, consecutively numbered envelopes constructed by the research assistant. Each envelope will have intervention sequence information. Sequence will be generated by a random number generator. The research assistant will assign 1 envelope to each subject randomly. Each envelope will be opened by the research assistant prior to first session who will administer tsDCS. The research assistant will not be involved in data analysis or measurement of outcomes.

Intervention (duration: three hours): This visit is divided in to baseline, tsDCS stimulation and post tsDCS.

Figure1 : Intervention Visit: Baseline H_{max}/M_{max} and SSEP will be performed before actual tsDCS intervention. Post

intervention Hmax/Mmax and SSEP will be performed after the tsDCS

Baseline: The baseline assessment will be performed on the same visit as intervention and will be performed in the Motor Recovery Laboratory by an evaluator blinded to subject's group assignment.

Vital Signs: Vital signs will be recorded at the beginning of each session.

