Baseline Hmax/Mmax		X		X		X		X		X
tsDCS		X		X		X		X		X
Post SSEP		X		X		X		X		X
Post Hmax/Mmax		X		X		X		X		X
Post Vital Signs		X		X		X		X		X
Questionnaire		X		X		X		X		X
Adverse Events		X		X		X		X		X

Table 1: Schedule of visits for SCI participant.

5. SUBJECT POPULATION:

Fifteen adults with SCI will be recruited from TIRR Memorial Hermann, TIRR Outpatient Rehabilitation at Kirby Glen and from the Houston area.

Inclusion Criteria:

1. Providing written informed consent prior to any study related procedures;
2. 18-65 years of age;
3. Motor incomplete SCI classified as B, C or D by the American Spinal Injury Association Impairment Scale (AIS);
4. Traumatic lesion at or above T8-T9 neurological level
5. Body mass index ≤ 30 (in order to facilitate reliable location of body landmarks guiding stimulation);
6. Chronic SCI (time since injury >6 months)

Exclusion Criteria: Subjects will be excluded if they have following conditions

1. Unstable cardiopulmonary conditions;
2. History of seizure, head injury with loss of consciousness, severe alcohol or drug abuse, and/or psychiatric illness;
3. Any joint contracture or severe spasticity, as measured by a Modified Ashworth Score 4;
4. Subject who cannot provide self-transportation to the study location;
5. Cardiac or neural pacemakers;
6. Pregnancy
7. h/o lower motor neuron injury (eg: peripheral neuropathy, cauda equina syndrome)
8. Uncontrolled diabetes with HbA1C >7 ;
9. History of severe autonomic dysreflexia;
10. alteration in therapy or medication for muscle tone during the course of the study (botulinum toxin injections in last 3 months, phenol injections in last 6 months, intrathecal baclofen pump dose stable for past 3 months, etc);
11. Conditions for e.g., severe arthritis, extreme shoulder pain that would interfere with valid administration of the measures or with interpreting motor testing;
12. contraindications to tsDCS:
- ferromagnetic material in the brain or in the spine (except for titanium used in segmental 9

fixation of the spine)

- implanted brain medical devices

6. SUBJECT ENROLLMENT:

Potential subjects will be identified by the following sources:

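### Exclusion item 10 words its baclofen pump example backwards: a stable dose is listed as a reason to exclude, and a recently changed dose is not named

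*Combined protocol and SAP*

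**What the plan says.** Section 5 opens the list with this rule: "Exclusion Criteria: Subjects will be excluded if they have following conditions". A person who has a listed condition is out.

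Item 10 has a lead-in and a bracket of examples:

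- The lead-in names "alteration in therapy or medication for muscle tone during the course of the study".
- The first two examples are "botulinum toxin injections in last 3 months, phenol injections in last 6 months".
- The third is "intrathecal baclofen pump dose stable for past 3 months, etc".

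Two other items come near the subject. Item 5 is "Cardiac or neural pacemakers". The first bullet of item 12 concerns "ferromagnetic material in the brain or in the spine". Neither mentions drug dose, and none of the six inclusion criteria requires a stable pump dose.

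Section 4 (Screening) states that "Demographics, medical history, list of medications and modified ashworth scale score will be recorded". It adds: "A medication diary will be given to the subject and asked to document all changes in type and dosage of the medication". Section 6, item 2, has staff ask about implants and medications by phone before the screening visit.

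**The concern.** The third example runs in the opposite direction to the other two. Recent toxin or phenol is a reason to exclude, while a dose held steady for 3 months is a reason to include. Under the opening rule, a stable-dose pump user matches a listed exclusion, and a candidate whose dose was changed last week matches no named one.

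Item 10 protects the main outcome. The background section links spasticity to alteration of the H-reflex, and Hypothesis 1 is tested on the Hmax/Mmax ratio. The stake is therefore who gets enrolled. Suitable candidates could be lost if staff apply the words as they stand, and recently adjusted subjects could be admitted, with some added variability in Hmax/Mmax. With 15 subjects, each wrong eligibility decision concerns one-fifteenth of the sample.

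**Working it through.** Whether the wording is wrong is a matter of reading. The arithmetic below only shows whether the gap could matter within the study's calendar.

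**Reading item 10 under its heading**

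| Part of item 10 | Period covered | Effect under the heading | Right direction? |
|---|---|---|---|
| Lead-in: alteration of tone therapy | During the study only | Exclude | Yes, but it does not look back |
| Botulinum toxin | Last 3 months | Exclude | Yes |
| Phenol | Last 6 months | Exclude | Yes |
| Pump dose stable | Past 3 months | Exclude | No, it describes an eligible subject |
| Closing *etc* | None given | Left to discretion | Not determinable |

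**Does anything else repair it?**

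- Item 5 covers pacemakers.
- Item 12 might catch some implants through its metal bullet, but it says nothing about dose.
- The lead-in refers to a period that has not begun at enrolment, so screening staff cannot apply it then.
- The medication diary is handed out at screening, so it does not record a change made earlier.

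**Timing**

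Inputs:

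- Wash-out: 1 week in the section 4 text; at least 8 days in Table 1.
- Screening: the same day as the intervention visit in the section 4 text; 0 to 30 days before it in Table 1.
- Five sessions, hence four wash-outs.
- Assumption: 3 months = 90 days.

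Session 1 to Session 5 at minimum spacing:

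- Text: 4 × 7 = 28 days.
- Table 1: 4 × 8 = 32 days.

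Screening to Session 5:

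- Same-day screening: 28 or 32 days.
- Screening 30 days earlier: 30 + 28 = 58 or 30 + 32 = 62 days.

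The range is 28 to 62 days. If the pump dose changed the day before screening, Session 5 falls 29 to 63 days after the change, which is under 90.

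The schedule sets only a minimum gap, so it is worth asking how wide the average spacing could be with all five sessions still inside the window:

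- Same-day screening: (90 − 1) / 4 = 22.25 days.
- Screening 30 days earlier: (90 − 31) / 4 = 14.75 days.

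Both exceed the 7- or 8-day minimum, so the result does not depend on the tightest schedule. A subject with a fresh dose change could complete every session inside the period the item was written to protect.

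**The case against.** The strongest reply is that the bracket only illustrates the lead-in, whose governing word is alteration. A stable dose is the opposite of an alteration, so a sensible reader takes the phrase as the stability expected of pump users and admits them. On that reading the 3-month window is stated after all. This stands as an account of intent and is why the point ranks low. It does not correct the text: the lead-in is limited to the study period, and staff who follow the intent must set aside the literal words.

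Second, eligibility is not decided mechanically. Section 4 requires final approval before a candidate comes for screening, and section 6 provides for review of the phone-screen information. This makes literal misapplication less likely, and it also stands.

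Third, no consequence for the estimates is shown. The outcome is a within-session difference, so slow drift after a dose change largely cancels. Condition order is randomised within subject, so drift is not systematically tied to polarity. The timing figures show only that exposure is possible. All of this is accepted, and no bias is claimed.

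Fourth, correcting the pump phrase leaves other tone medication changed before enrolment without a window. That is true. It is a limit of the minimal correction, not a reason to leave the reversed phrase in place.

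**Conclusion.** The concern holds. The pump example is worded in the wrong direction for an exclusion list, and no criterion names a pump dose changed in the 3 months before enrolment. Confidence is high on the wording.

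The consequence is probably small: perhaps some added variability in Hmax/Mmax, and perhaps some eligible candidates turned away. Neither can be quantified, because the number of pump users is not given and the documents offer nothing from which to compute an effect. The timing result rests on taking 3 months as 90 days and on the spacing stated in the protocol. No hazard from giving stimulation to pump users is claimed. This is a low-priority correction, worth making because it is an operative eligibility rule and easily put right.

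**What to change.** Reword the third example in item 10 as *intrathecal baclofen pump dose changed in past 3 months*. All three examples are then reasons to exclude, each with its own look-back window.

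The lead-in can stay as it is. If the sponsor prefers, it can be extended to cover alterations within the bracketed windows as well as those during the study. Item 12 needs no change, and whether pump users should receive tsDCS at all is a separate decision for the sponsor.

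The cost is one phrase and at most one extra screening question, the date of the last pump dose change. Implants and medications are already asked about by phone, and medical history and a medication list are already taken at screening. A candidate with a recent dose change would wait until 3 months have passed. Design, sample size and analysis are unaffected.
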